5.3. Relationship to OTX-TP or PV

The following table will be used by the investigator as a guide when assessing the causal relationship of an adverse event to the intracanalicular depot and the insertion procedure.

NO RELATIONSHIP SUSPECTED	This category applies to those adverse events which, after careful consideration, are clearly and incontrovertibly due to extraneous causes (disease, environment, etc.)
RELATIONSHIP SUSPECTED	
The following criteria should be applied in considering inclusion of an adverse event in this category:
 
 1) It bears a reasonable temporal relationship to the insertion procedure or the presence of the intracanalicular depot. 2) It could not be reasonably explained by the known characteristics of the subject's clinical state, environmental or toxic factors or other modes of therapy administered to the subject. 3) It disappears or decreases on removal of the intracanalicular depot. 4) It follows a known pattern of response to the insertion procedure or the intracanalicular depot.
UNABLE TO DETERMINE*	The Investigator is unable to assess the relationship of the event to the insertion procedure or the intracanalicular depot.

*Where the causal relationship of the AE to the insertion procedure or the intracanalicular depot has not been determined or is unknown, the AE will be treated as if a relationship is suspected for the purposes of regulatory reporting.
	

Suspected adverse reaction means any adverse event for which there is a reasonable possibility that the study drug caused the adverse event. "Reasonable possibility" means there is evidence to suggest a causal relationship between the study drug and the adverse event. Types of evidence that would suggest a causal relationship between the study drug and the adverse event include: a single occurrence of an event that is uncommon and known to be strongly associated with drug exposure; one or more occurrences of an event that is not commonly associated with drug exposure, but is otherwise uncommon in the population exposed to the drug (e.g., tendon rupture); an aggregate analysis of specific events observed in a clinical trial (such as known consequences of the underlying disease or condition under investigation or other events that commonly occur in the study population independent of drug therapy) that indicates those events occur more frequently in the drug treatment group than in a concurrent or historical control group.

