- is life-threatening (The term "life-threatening" in the definition of "serious" refers to an event in which the subject was at risk of death at the time of the event; it does not refer to an event which hypothetically might have caused death if it were more severe.)
- requires inpatient hospitalization or prolongation of existing hospitalization
- results in persistent or significant disability/incapacity
- is a congenital anomaly/birth defect
- is sight-threatening

Medical and scientific judgment will be exercised in deciding whether expedited reporting is appropriate in other situations, such as important medical events that may not be immediately life-threatening or result in death or hospitalization but may jeopardize the subject or may require intervention to prevent

one of the other outcomes listed in the definition above. These should also usually be considered serious.

Severity

Severity of an AE is defined as a qualitative assessment of the degree of intensity of an AE as determined by the Investigator or reported to him/her by the subject. The assessment of severity is made irrespective of relationship to study drug or seriousness of the event and should be evaluated according to the following scale:

Mild: Event is noticeable to the subject, but is easily tolerated and does not interfere with the subject’s daily activities.

Moderate: Event is bothersome, possibly requiring additional therapy, and may interfere with the subject’s daily activities.

Severe: Event is intolerable, necessitates additional therapy or alteration of therapy, and interferes with the subject’s daily activities.¹

¹The term “severe” is often used to describe the intensity (severity) of a specific event (as in mild, moderate, or severe myocardial infarction); the event itself, however, may be of relatively minor medical significance (such as severe headache). This is not the same as “serious”, which is based on the outcome or action criteria usually associated with events that pose a threat to life or functioning. Seriousness (not severity) and causality serve as a guide for defining regulatory reporting obligations. (Severity of all adverse events, ocular and non-ocular, will be reported according to the terminology defined in the protocol.)

Relationship to OTX-TP or PV

The following table will be used by the investigator as a guide when assessing the causal relationship of an AE to the intracanalicular depot and the insertion procedure.

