NO RELATIONSHIP SUSPECTED	This category applies to those adverse events which, after careful consideration, are clearly and incontrovertibly due to extraneous causes (disease, environment, etc.)
RELATIONSHIP SUSPECTED	
The following criteria should be applied in considering inclusion of an AE in this category:
 
 1) It bears a reasonable temporal relationship to the insertion procedure or the presence of the intracanalicular depot. 2) It could not be reasonably explained by the known characteristics of the subject’s clinical state, environmental or toxic factors or other modes of therapy administered to the subject. 3) It disappears or decreases on removal of the intracanalicular depot. 4) It follows a known pattern of response to the insertion procedure or the intracanalicular depot.

UNABLE TO DETERMINE*	The Investigator is unable to assess the relationship of the event to the insertion procedure or the intracanalicular depot.
*Where the causal relationship of the AE to the insertion procedure or the intracanalicular depot has not been determined or is unknown, the AE will be treated as if a relationship is suspected for the purposes of regulatory reporting.	

Suspected adverse reaction means any adverse event for which there is a reasonable possibility that the study drug caused the AE. “Reasonable possibility” means there is evidence to suggest a causal relationship between the study drug and the AE. Types of evidence that would suggest a causal relationship between the study drug and the adverse event include: a single occurrence of an event that is uncommon and known to be strongly associated with drug exposure; one or more occurrences of an event that is not commonly associated with drug exposure, but is otherwise uncommon in the population exposed to the drug (e.g., tendon rupture); an aggregate analysis of specific events observed in a clinical trial (such as known consequences of the underlying disease or condition under investigation or other events that commonly occur in the study population independent of drug therapy) that indicates those events occur more frequently in the drug treatment group than in a concurrent or historical control group. For TEAEs not suspected to be related to study product, a most likely cause will be selected from the following categories: Concomitant Medication(s), Pre-existing Condition(s), Insertion Process, Other.

Expected AEs

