Separate summaries will be provided for the following categories of AEs:

- Ocular TEAEs in the primary study eye
- Ocular TEAEs in the secondary study eye
- Non-ocular TEAEs
- Expected TEAEs
- Unexpected TEAEs
- Treatment related ocular TEAEs
- Treatment related non-ocular TEAEs
- Serious AEs
- TEAEs by Maximum Severity
- Non-related TEAEs by Most Likely Cause
- Non-related SAEs by Most Likely Cause
- Ocular TEAEs of Special Interest

The following Preferred Terms are considered TEAEs of Special Interest:

- Conjunctival hyperaemia
- Ocular hyperaemia
- Iritis
- Cystoid macular oedema
- Eye colour change

- Madarosis
- Eyelash discolouration
- Eyelash hyperpigmentation
- Eyelash injury
- Growth of eyelashes

All TEAEs, SAEs and TEAEs leading to subject withdrawal from the study will be presented in subject listings separately for ocular and non-ocular events.

Best Corrected Visual Acuity (BCVA)

The logarithm of the minimum angle of resolution (logMAR) visual acuity is assessed at each visit using an EDTRS chart at a viewing distance of 4 meters. BCVA will be measured without refraction using a pinhole or while the subject is wearing his/her glasses, if the subject normally wears glasses or contact lenses. Subjects are required to read the chart from the top to the bottom until 2 letters are misread on the line. The visual score is to be calculated based on an assigned value of 0.02 logMAR per letter. If visual acuity is so poor that the subject cannot read any of the largest letters at 4 meters, then acuity is to be measured at 2 meters and the appropriate conversions made.

If visual acuity is so poor that the subject cannot read any of the largest letters at 2 meters, the subject should be checked for the ability to count fingers or see hand motion or light perception as appropriate.

BCVA will be measured at screening, at 8AM on Baseline Visit 2 and as well as the 8AM time point at each post-baseline visit. The baseline measurement will be the last assessment prior to insertion of the depot.

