Table 14.2.1.8	Mean Observed, Change, and Percent Change from Baseline in Secondary Study Eye IOP by Time Point Observed Data Analysis	Full Analysis Set
Table 14.2.1.9	Mean Observed, Change, and Percent Change from Baseline in Secondary Study Eye IOP by Time Point Observed Data Analysis	Per Protocol Population
Table 14.2.2.1	Mean Observed, Change, and Percent Change from Baseline in Primary Study Eye IOP by Time Point and Strata MCMC Analysis	Full Analysis Set
Table 14.2.4.1	Insertion Results and Ease of Insertion	Safety Population
Table 14.2.4.2	Summary of Replacements	Safety Population
Table 14.2.4.3	Removal of Intracanalicular Depot	Safety Population
Table 14.2.5	Ocular Complaints by Study Eye	Safety Population
Table 14.2.6	Investigator Visualization of Intracanalicular Depot	Safety Population
Table 14.2.7	Punctum Examination Results	Safety Population
Table 14.3.1	Study Treatment Exposure	Safety Population
Table 14.3.2.1	Overall Summary of Adverse Events	Safety Population
Table 14.3.2.2.1	Non-Ocular Treatment Emergent Adverse Events by System Organ Class and Preferred Term	Safety Population
Table 14.3.2.2.2	Ocular Treatment Emergent Adverse Events by System Organ Class and Preferred Term	Safety Population
Table 14.3.2.2.3	Primary Study Eye Ocular Treatment Emergent Adverse Events by System Organ Class and Preferred Term	Safety Population

Table Number	Title	Population
Table 14.3.2.2.4	Secondary Study Eye Ocular Treatment Emergent Adverse Events by System Organ Class and Preferred Term	Safety Population
Table 14.3.2.2.5	Treatment Related Ocular Treatment Emergent Adverse Events by System Organ Class and Preferred Term	Safety Population
Table 14.3.2.2.6	Treatment Related Non-Ocular Treatment Emergent Adverse Events by System Organ Class and Preferred Term	Safety Population
Table 14.3.2.2.7	Serious Adverse Events by System Organ Class and Preferred Term	Safety Population
Table 14.3.2.2.8	Treatment Emergent Adverse Events Leading to Subject Withdrawal by System Organ Class and Preferred Term	Safety Population
Table 14.3.2.2.9	Ocular Treatment Emergent Adverse Events of Special Interest by System Organ Class and Preferred Term	Safety Population
Table 14.3.2.3	Treatment Emergent Adverse Events by System Organ Class, Preferred Term, and Maximum Severity	Safety Population
Table 14.3.2.4	Non-Related Treatment Emergent Adverse Events by System Organ Class, Preferred Term, and Most Likely Cause	Safety Population

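### SAP v2.0 lets an event caused by insertion be reported as non-related, although its causality scale covers the insertion procedure

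*SAP*

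**What the plan says.** SAP v2.0 section 14, under Relationship to OTX-TP or PV, gives the investigator a table as a guide for "assessing the causal relationship of an AE to the intracanalicular depot and the insertion procedure". Protocol section 5.3 has the same table with the same scope.

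- **Relationship suspected** has four criteria to consider. The first is "It bears a reasonable temporal relationship to the insertion procedure or the presence of the intracanalicular depot". The fourth is "It follows a known pattern of response to the insertion procedure or the intracanalicular depot".
- **No relationship suspected** is for events that, after careful consideration, "are clearly and incontrovertibly due to extraneous causes (disease, environment, etc".)
- **Unable to determine** carries a footnote: "the AE will be treated as if a relationship is suspected for the purposes of regulatory reporting".

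The SAP subsection closes with a sentence that Protocol 5.3 does not have. It concerns TEAEs judged not related to study product, and states that "a most likely cause will be selected from the following categories: Concomitant Medication(s), Pre-existing Condition(s), Insertion Process, Other".

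Under AE Summaries, the same SAP section plans summaries of non-related TEAEs by cause and of "Non-related SAEs by Most Likely Cause". Section 22 lists the first as Table 14.3.2.4, "Non-Related Treatment Emergent Adverse Events by System Organ Class, Preferred Term, and Most Likely Cause". The treatment-related ocular and non-ocular TEAEs are Tables 14.3.2.2.5 and 14.3.2.2.6. The overall summary, Table 14.3.2.1, has a line for related TEAEs.

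**The concern.** The scale counts insertion as a possible source of relatedness, while the cause list counts it as an explanation for an event that is not related. Two sites could see the same injury and send it to opposite tables without either one clearly breaking the SAP.

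The product cannot be used without being inserted, so harm from insertion is part of the harm of treatment. A vehicle-depot control cannot expose it, because control subjects undergo the same procedure. Procedural harm therefore has to be read from the absolute related-event counts, and those are the counts that can come out too low.

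**Working it through.** No arithmetic applies, because the plan states no figure on this point. The check is whether the provisions can all hold at once, and where an event then lands.

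**1. Scope of the scale.** Both documents assess relationship to the depot and to the insertion procedure on a single scale. Two of the four criteria for a suspected relationship name the insertion procedure.

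**2. What may be called not related.** Only events clearly due to something extraneous, with disease and environment as examples. On a scale that includes insertion, insertion is not extraneous.

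**3. The cause list.** It applies only after an event has been judged not related, and *Insertion Process* is one of its four choices. By steps 1 and 2, an event whose most likely cause is insertion should not have reached this list. The list and the scale contradict each other.

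**4. Tracing one event.** Trauma to the punctum is on the list of anticipated ocular events (Protocol 5.5.1, repeated in SAP section 14). Suppose it occurs at insertion:

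| Output | Marked *Relationship suspected* | Marked not related, cause *Insertion Process* |
|---|---|---|
| Ocular TEAE tables 14.3.2.2.2 to 14.3.2.2.4, ocular AE listing | included | included |
| Related-TEAE line, Table 14.3.2.1 | included | absent |
| Table 14.3.2.2.5 (14.3.2.2.6 for a non-ocular event) | included | absent |
| Table 14.3.2.4, non-related by cause | absent | included |

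A serious event stays in Table 14.3.2.2.7 either way, but in the second case it also enters the non-related serious-event summary. That summary is planned in the text and has no table number in section 22.

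**5. Looking for a provision that reconciles the two.** There is no second scale for procedure-relatedness and no planned table of procedure-related events. Neither document says which causality categories make up treatment-related. The cause list is absent from the protocol, appears in SAP v1.0 and v2.0, and is not among the departures from the protocol listed in SAP v2.0 section 19.

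**6. How insertion is treated elsewhere.** Treatment emergence starts when depot insertion is initiated (SAP section 14). Protocol 4.7.1 lists risks of inserting the depot together with risks of using it. Both treat insertion as part of treatment.

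**The case against.** **Few events need be affected.** The cause list is reached only when an investigator has already marked an event as not related. One who follows the scale will mark an insertion injury as suspected or undetermined, and it never reaches the list. This stands. Only events from sites that depart from the scale, or that read study product as the depot alone, can move.

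**The criteria are a guide.** Neither document says that meeting one criterion is enough, and an insertion injury need not resolve when the depot is removed, which is the third criterion. This also stands, so it cannot be said that every event close in time to insertion must be rated as suspected. The contradiction does not depend on that. It arises once insertion is recorded as the most likely cause, because insertion is then hard to describe as extraneous.

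**Study product may mean the depot only.** This is the best reconciling reading. It fails because procedure-relatedness is assessed nowhere else, and on that reading insertion injuries would still sit under a non-related heading and outside the related tables.

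**The events stay visible and can be added back.** Visibility is a fair point. Adding back is only partly possible from the tables. The related-event tables report subjects and count a preferred term once per subject, so a subject could appear in both a related and a non-related table. The number of subjects with at least one related event then needs subject-level data.

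**Relatedness is the investigator's judgement.** Agreed. The remedy should change what is tabulated and leave the recorded assessment alone.

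**Conclusion.** The two provisions contradict each other and need to be reconciled before the related-event tables are produced. The consequence is limited: the absolute rate of treatment- or procedure-related events can be understated in both arms, to an extent the documents do not allow anyone to estimate. This assumes only that at least some sites use the *Insertion Process* option the SAP gives them. Efficacy, type I error and power are unaffected.

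Four stronger readings are tempting, and the documents do not support them.

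- *A count of misplaced events.* A reader might apply an assumed 1% to 3% to the planned 1,100 eyes and arrive at 11 to 33 events. Neither document gives a rate of insertion injury, and the figure also assumes that every such event is marked not related.
- *Bias between arms.* Both arms undergo the same masked insertion, and nothing in the documents suggests that misclassification would differ by arm.
- *Serious events escaping oversight.* Protocol 5.5 sends all serious events to the sponsor within 24 hours whatever their relatedness, and has investigators inform the IRB under its own guidelines. Relatedness matters in one reporting sentence there, and a SAP cause category does not amend it.
- *Undetermined events must be tabulated as related.* The footnote is confined to regulatory reporting. It does not settle how the tables count them.

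**What to change.** 1. In SAP section 14, define treatment-related as related to the depot or to the insertion procedure, so that the scale and the cause list agree.
2. In Tables 14.3.2.1, 14.3.2.2.5 and 14.3.2.2.6, and for serious events, count every event rated *Relationship suspected* or given *Insertion Process* as its most likely cause. Show depot-related and procedure-related events in separate rows.
3. Do not show *Insertion Process* events under a non-related heading, in Table 14.3.2.4 or in the serious-event summary by cause.
4. Keep the investigator's assessment as recorded in the listings, so that the derivation can be traced.

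The cost is SAP wording and a derivation rule. The SAP already calls for a cause to be selected, so the combined count needs no new assessment, although the case report form itself is not in the documents. One limit applies to the split. For an event rated *Relationship suspected*, the single scale does not record whether depot or procedure was meant. Either sites record this, or the first row is labelled as depot or not specified. The downside is that related-event counts become slightly less favourable.
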